11.1 SOURCES OF MATERIAL

Research material obtained from identifiable living human subjects includes reports of: history and physical assessments, blood, urine, chest X-ray, ECHO, EKG, EIM, pulmonary function tests, and MRI, clinical assessments and admission/ discharge summaries for hospitalization occurring while the subject is on study, adverse events, and autopsies. Copies of case report forms, original test results, subject medical records, signed subject informed consent, correspondence, and any other documents of the subjects, relevant to the conduct of the study will be kept on file by the Principal Investigator. All material or data collected as part of the study will be obtained specifically for research purposes.

11.2 POTENTIAL RISKS

Potential risks to study subjects include risks associated with administration of the study agent and with study procedures.

11.2.1 RISKS ASSOCIATED WITH rAAV.CMV.HUFS344 GENE TRANSFER

There is a very small chance that the study agent could damage the DNA in the cells of the subject's muscle. In the unlikely event that this occurred, it could put the subject at risk for developing cancer in the future. In animal studies to date, we have not seen the development of cancer. In addition, we and others have shown that the majority of vector DNA appears to persist as episomal rather than integrated DNA, which makes it very unlikely that mutagenesis will occur.⁵⁴⁻⁵⁶ In summary, our data suggest that AAV genomes persist in mouse muscle as transcriptionally active large and small concatameric episomes and when considering potential and theoretical integration events, AAV vectors appear to possess a similar risk profile as plasmid DNA injected into muscle.⁵⁵ The majority of vector DNA appears to persist as episomal rather than integrated DNA, which makes it very unlikely that mutagenesis will occur.⁵⁴

Liver tumors were reported in one study performed in newborn mice at another center with a different rAAV vector. There is no evidence to indicate that these tumors were caused by

vector-induced DNA damage based on the number of AAV genomes per cell in tumor samples. ^{57, 58} Also, other larger scale studies in newborn and adult mice have not shown this effect. ⁵⁹ It remains difficult to ascertain the true risk of neoplasia, although it seems very small.

Subjects may also develop immune response to AAV1. This could lead to immune rejection of virus precluding gene expression. We will measure both binding antibodies and T cell responses to the AAV capsid following gene transfer.

11.2.2 RISKS ASSOCIATED WITH PROCEDURES

11.2.2.1 BLOOD DRAWS

The risks of venous blood draws include discomfort at the site of puncture; possible bruising and swelling around the puncture site; rarely an infection; and, uncommonly, fainting, nausea, vomiting, and light-headedness from the procedure.

11.2.2.2 GENE TRANSFER TO MUSCLES

In this trial, patients will receive at least 18 injections per extremity. This will be done under sterile conditions by the PI accompanied by the ultrasonographer. Both will be gowned and gloved. Patients will also receive conscious sedation that will be directed by the anesthesiologist at Nationwide Children's Hospital. There is a low risk of complications that could include hypotension, respiratory compromise, and complications from low blood pressure such as stroke or myocardial infarction. These would be rare and unlikely complications of the procedure.

11.2.2.3 MUSCLE BIOPSY

The muscle biopsy has potential complications from procedure that include infection at the biopsy site, bleeding and/or pain at the site of the biopsy, and psychological trauma from the scar at the site of the incision; in some cases because of keloid formation this can be quite large.

11.2.2.4 STEROIDS

The possible side effects of prednisolone or Deflazacort (steroids) include acne, increased hair growth, thinning of the skin, glaucoma, roundness of the face, changes in behavior, disturbance of sleep, and increase of blood glucose level.

11.3 ADEQUACY OF PROTECTION AGAINST RISKS

11.3.1 INFORMED OF RISKS

Volunteer subjects will be recruited from the Nationwide Children's Hospital, Columbus-MDA Clinic or self-referred in response to advertisement. This protocol will also be listed in the Clinical Trials Data Bank of the NIH. Potential study subjects who demonstrate an interest in participating in the study will receive a copy of the informed consent form to review and an explanation of the nature, duration, and purpose of the study and possible consequences of the study from one of the investigators in a language they can understand. They will be informed that they may withdraw from the study at any time and for any reason without jeopardizing their future treatment. They will be asked to follow-up with necessary safety evaluations if they have received study agent prior to their desire to withdraw. They will be given full information regarding potential side effects of rAAV1 and follistatin gene. Subsequently, an investigator will request the subject's permission to participate in the study. Volunteer participants who sign the study specific subject informed consent form approved by the Institutional Review Board of Nationwide Children's Hospital will be screened for eligibility to participate in the gene transfer study.

11.3.2 MINIMIZATION OF POTENTIAL RISK

Participants will be provided with contact numbers for any questions or concerns arising regarding the possible effects of the administration of rAAV1.CMV.huFS344. Results of all laboratory and safety exams regarding subject enrollment and following gene transfer will be reviewed with the subject. Since the effects on the reproductive system are not fully established and the possible concerns with viral shedding, subjects with reproductive capacity must be willing to refrain from sexual intercourse or use effective contraception for the active phase of the study until two negative sperm samples are obtained post gene transfer (males).

Some of the vector can be excreted from the body for a least a week after injection. This shedding of vector can be found in the blood, urine, saliva, and stool for up to a week following injection. For a period of two weeks after gene injection, people who may come into contact with participants' bodily fluids and waste must regularly wash their hands with soap and those who will have direct contact with their bodily fluids and waste must were protective gloves.

11.3.3 CONFIDENTIALITY

Access to the database will be limited to the key research personnel to ensure confidentiality. Case report forms, informed consent forms, laboratory study reports, and demographic profiles will be kept locked in a secure record storage and archiving under the responsibility of research staff. The subjects will be informed of what information is stored and of the secured access to their information by the following regulatory bodies: FDA-CBER, IRB, IBCSC, NCH internal monitors, and an outside contracted monitor designated for the study called a "CRO". Subjects will be alerted that others may have an interest in the innovative character of the protocol and in the status of the treated subjects. They will be informed that the institution and investigators will make efforts to provide protection from the media in an effort to protect the participants' privacy. They will be consulted as to whether, when, or how their identity is publicly disclosed.

11.3.4 PROVISIONS FOR INJURY

If a subject experiences an injury that is directly related to this study, the event will be followed up until its resolution. Nationwide Children's Hospital will provide medical treatment reasonably necessary for such injury or illness at no cost to the subject or his insurance company for medical expenses up to \$10,000. In order for The Research Institute at Nationwide Children's Hospital to pay for these medical expenses the illness or injury must not be related to subject's underlying medical condition and subject must have followed the study directions.

If research subject seeks care for a research related injury or illness from a medical provider other than Nationwide Children's Hospital, then The Research Institute at Nationwide Children's Hospital will pay up to \$10,000 to reimburse the research subject for treatment of such injury or illness directly resulting from the study. Any claim for reimbursement must be supported by documentation such as a bill or invoice from a medical provider. In order for The Research Institute at Nationwide Children's Hospital to pay for these medical expenses the research subject's illness or injury must not be related to his/her underlying medical condition and research subject must have followed the study directions.

The Research Institute at Nationwide Children's Hospital's reimbursement for injury or illness as a result of research subject's participation in the study does not include any payment for lost wages, lost time, emotional distress or pain. This does not mean that the research subject gives up any of his legal rights to seek compensation for his illness or injury.

11.4 POTENTIAL BENEFITS OF RESEARCH TO SUBJECTS AND OTHERS

This is primarily a safety study of transfer of rAAV1.CMV.huFS344. Based on the results of the BMD clinical trial using the same vector, subjects participating in this trial could improve their walking ability. There is also anticipated benefit to determine the safety of this vector system that may provide efficient and sustained efficacy.

11.5 INCLUSION OF MINORITIES

11.5.1 SELECTION CRITERIA

Six DMD subjects will be enrolled in this trial. Eligibility criteria will include subjects (age 7 and older) with proven DMD mutations. Participants will encompass any ethnic or racial background.

11.5.2 TARGETED / PLANNED ENROLLMENT

The number of subjects enrolled from each ethnic group will mirror that seen in the clinic population.

Local Distribution of Disease (Percent)

Gender	American Indian Alaskan Native	Asian or Pacific Islander	Hispanic	Black, Non- Hispanic	White, Non- Hispanic	Total
Female	0	0	0	0	0	0
Male	0	0.7	1.4	0.7	97.2	100
Total	0	0.7	1.4	0.7	97.2	100

11.5.3 PROPOSED DATES OF ENROLLMENT AND RECRUITMENT

We anticipate beginning enrollment in Winter 2014, with completion of enrollment December 2015. This protocol will be listed in the Clinical Trials Data Bank of the NIH.

12.0 DATA AND SAFETY MONITORING PLAN

12.1 THE DATA SAFETY MONITORING BOARD

The Data and Safety Monitoring Board (DSMB) will act in an advisory capacity to review participant safety and study progress for the "Phase I/II gene transfer clinical trial for Duchenne Muscular Dystrophy using rAAV1.CMV.huFS344."

Responsibilities of the DSMB are to:

- Review the research protocol, informed consent documents and plans for data and safety monitoring;
- Evaluate the progress of the trial, including periodic assessments of data quality

and timeliness, participant recruitment, accrual and retention, participant risk

versus benefit, trial site performance, and other factors that can affect study outcome;

- Consider factors external to the study when relevant information becomes available, such as scientific or therapeutic developments that may have an impact on participant safety or the ethics of the trial;
- Review study performance, make recommendations and assist in the resolution of problems reported by the Principal Investigator;
- Protect the safety of the study participants;
- Review safety data to determine whether to recommend dose escalation;
- Ensure the confidentiality of the trial data and the results of monitoring; and,

• Assist by commenting on any problems with study conduct, enrollment, and sample size and/or data collection.

DSMB Reporting and Meetings

Reports describing the status of the study will be prepared by the Principal Investigator's staff and sent to the DSMB at the end of each cohort, or at the DSMB's request.

An initial meeting (either by teleconference or webcast) with the DSMB will be scheduled prior to study initiation and after Day 30 visit of the first subject, and approximately every 6 months thereafter, or at the DSMB's request. Reports will be submitted prior to a scheduled meeting for review by the DSMB.

Reports will include the following:

A brief narrative of the study status, including the target enrollment, current and projected time to completing enrollment. Any significant events and/or difficulties should be briefly described in this narrative.

- A brief narrative for each participant describing age, race and ethnicity and other relevant demographic characteristics. The narrative for each participant should briefly describe his study status (i.e., dose level, visit number, adverse event information);
- A timeline outlining the study progress relative to visit number for each participant, as well as time points for each SAE/Dose Limiting Toxicity. A total for Adverse Events (AEs) for each participant should be included.
- A summary of AEs by severity levels;
- A listing of AE details grouped by participant;
- A listing of SAE details grouped by participant;
- A listing of deaths
- A summary of clinically significant laboratory test results
- A listing of protocol deviations

Stopping/Discontinuation Rules

An independent Data Safety Monitoring Board (DSMB) will be designated by the study's sponsor. Safety data will be monitored on a continual basis throughout the trial. The DSMB can recommend early termination of the trial for reasons of safety. Study enrollment will be halted by the investigators when any subject experiences a Grade 3 or higher adverse event toxicity that is possibly, probably, or definitely related to the study drug. This will include any subject death,

important clinical laboratory finding, or any severe local complication in the injected area related to administration of the study agent. If after review by the DSMB, IRB,

IBCSC, NIH-OBA and FDA, the decision is made to continue, the study will proceed according to Dose Escalation plan.

MEMBERSHIP

The DSMB membership consists of persons completely independent of the investigator who have no financial, scientific, or other conflicts of interest with the trial. Current or past collaborators or associates of [name] must note any conflict of interest before their eligibility to serve on the DSMB is approved.

The DSMB will include experts in or representatives of the fields of:

- Neurology and Neuromuscular Diseases
- Immunology
- Gene Therapy
- Muscular Dystrophy Clinical Care
- Clinical Research and Clinical Trials

Conflict of Interest

Individuals invited to serve on the DSMB as either voting or non-voting members must disclose any potential conflicts of interest, whether real or perceived. Conflicts of interest can include professional, proprietary, and miscellaneous interests as described in the NIH Grant Policy Statement and 45 CFR Part 94. Potential conflicts that develop during a member's tenure on a DSMB must also be disclosed. Written documentation attesting to an absence of conflict of interest is required.

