7.3 DOSE LIMITING TOXICITY

In reporting adverse events we will follow the final regulations issued by the Food and Drug Administration addressing the safety reporting requirements for investigational new drug applications (INDs) found in 21 CFR part 312 and for bioavailability and bioequivalence studies found in 21 CFR part 320. "Safety Reporting Requirements for INDs and BA/BE Studies".

The classification for adverse events to be used is the following:

- 1 Mild adverse event; did not require treatment
- 2 Moderate adverse event; resolved with treatment
- 3 Severe adverse event; inability to carry on normal activities; required professional medical attention
- 4 Life-threatening or permanently disabling adverse event
- 5 Fatal adverse event In this grading system, "severe" is not equivalent to *seriousness*.

The definitions to be employed will follow the final regulations issued by the FDA in September 2010 "Safety Reporting Requirements for INDs and BA/BE Studies.

Dose limiting toxicity (DLT) is defined as any adverse event that is possibly, probably, or definitely related to the study agent. This would include any grade 3 according to the classification given above. Study enrollment will be halted by the investigators when any subject experiences a Grade 3, or higher adverse event toxicity that is possibly, probably, or definitely related to the study drug.

Laboratory tests with values within the clinically significant range will be repeated during the same visit whenever possible. If the test result returns after the subject leaves the clinic, they will be immediately contacted. For local residents they will be asked to return to the outpatient clinic for a repeat test. For non-local residents, arrangements will be made to have the blood test redrawn in a laboratory close to home or by their primary care physician. To avoid any confusion for the primary care physician, they will be informed (with permission from the subject) of their participation in the study at the time of gene transfer. If the AE requires treatment, this will be carried out by the primary care physician or a doctor of choice selected by the subject. We will obtain copies of repeat laboratory tests and any relevant medical records that will be added to the subject's research chart.

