Only those adverse events requiring treatment will qualify as DLT. The PI will fulfill the reporting responsibilities under 21 CFR 312.32(c), to notify FDA in an IND safety report of potentially serious risks, as soon as possible, but no later than 15 calendar days after the

investigator receives the safety information and determines that the information qualifies for reporting. The investigator will confer with the DSMB, IRB, IBCSC, CBER, FDA, OBA, and NIH before continuing enrollment.

Test	Units	Reference Range		Clinically Significan Range		
Hemoglobin	g/dL	2Y - 5Y	11.5 - 13.5	< 8.0 or > 18		
0	-	6Y - 11Y	11.5 - 15.5			
		12Y – Adult	12.0 - 16.0			
WBC	K/cu mm	4Y - 5Y	5.5 - 15.5	$\leq 3.5 \text{ or} \geq 20$		
		6Y - 9Y	5.0 - 14.5			
		10Y - 20Y	4.5 - 13.5			
		21Y – Adult	4.5 - 11.0			
BUN	mg/dL	5 - 18		≥35		
РТ	sec	12.4 - 14.7		\leq 5.0 or \geq 35.0		
PTT	sec	24 - 36		≥ 125		
Platelet	K/cu mm	140 - 440		\leq 90 or \geq 800		
Amylase	U/L	0 - 17Y	<110	\geq 200		
		18Y – Adult	30 - 110			
Total Protein	g/dL	3Y - 15Y	5.8 - 8.7	$\leq 4.4 \text{ or} \geq 9.5$		
		16Y – Adult	6.4 - 8.4			
Total Bilirubin	mg/dL	0.1 – 1.0 mg/dL		≥ 3.0		
Creatinine	mg/dL	4Y - 7Y	0.3 - 0.8	≥ 1.8		
	Ū.	8Y - 10Y	0.3 - 0.9			
		11Y - 12Y	0.4 - 1.0			
		13Y - 17Y	0.5 - 1.2			
		18Y – Adult	0.6 - 1.3			
GGT*	U/L	8 - 78		3XULN		
ULN= upper limit r	normal					

Table of Clinically Significant Laboratory Ranges

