7.4 STOPPING AND DISCONTINUATION RULES

An independent Data Safety Monitoring Board (DSMB) will be established by the sponsoring agency including a safety monitor for the study. Safety data will be monitored on a continual basis throughout the trial. The DSMB can recommend early termination of the trial for reasons of safety. Study enrollment will be halted by the investigators when any subject experiences a Grade 3, or higher adverse event toxicity that is possibly, probably, or definitely related to the study drug. This will include:

Grade 3 Severe or medically significant but not immediately life-threatening; hospitalization or prolongation of hospitalization indicated; disabling; limiting self care ADL**.

Grade 4 Life-threatening consequences; urgent intervention indicated.

Grade 5 Death related to AE.

Activities of Daily Living (ADL)

*Instrumental ADL refer to preparing meals, shopping for groceries or clothes, using the

telephone, managing money, etc.

**Self care ADL refer to bathing, dressing and undressing, feeding self, using the toilet, taking

medications, and not bedridden.

If after review by the DSMB, IRB, IBCSC, NIH-OBA and FDA, the decision is made to continue according to this study protocol.

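### The DSMB meeting after the first boy's day 30 visit has no latest date and holds back no later gene transfer, so further boys can be dosed before it

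*Combined protocol and SAP*

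**What the plan says.** Section 12.1 plans DSMB meetings that "will be scheduled prior to study initiation and after Day 30 visit of the first subject", then about every six months or when the DSMB asks. Status reports are "sent to the DSMB at the end of each cohort" or on request. Section 7.2 gives all six boys the same dose, so no cohort ends before the sixth boy.

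Sections 6.3, 7.2, 7.3, 7.4 and 12.1 contain no minimum interval between boys, no waiting period after the first boy and no DSMB clearance step.

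Control of further enrollment is driven by events:

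- Section 7.4: "Study enrollment will be halted by the investigators when any subject experiences a Grade 3, or higher adverse event toxicity" with at least a possible relation to the agent. Section 12.1 adds an "important clinical laboratory finding, or any severe local complication in the injected area related to administration of the study agent".
- Section 7.3: "Dose limiting toxicity (DLT) is defined as any adverse event that is possibly, probably, or definitely related to the study agent", later narrowed by "Only those adverse events requiring treatment will qualify as DLT". It adds: "The investigator will confer with the DSMB, IRB, IBCSC, CBER, FDA, OBA, and NIH before continuing enrollment". Section 8.3 sends serious events and DLTs to the DSMB within 48 hours. On this wording, a related Grade 2 event that needed treatment also reaches the DSMB quickly.
- Sections 7.4 and 12.1 provide continual safety monitoring, and section 13.1 has a safety monitor who reviews case report forms regularly.

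The DSMB report lists adverse events by participant and severity and includes "A summary of clinically significant laboratory test results". It does not name the immunology or circulating follistatin results, and the section 7.3 table has no threshold for either. In the section 6.7 timeline, immunology is sampled on days 7, 14 and 30. Circulating follistatin is first measured after dosing on day 30.

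**The concern.** Safety is the primary objective (section 4.1). The vector is given in one procedure (section 6.3), and section 11.2.1 expects its DNA to persist, so a dose cannot be taken back. The total dose per kilogram is twice the highest in the Becker trial and goes to three muscle groups per leg instead of one. Section 5.0 attributes remote effects in mice injected in several muscles to circulating follistatin, and reports none in primates injected in one muscle.

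The sponsor has already planned an early look at the first boy. That look can inform every later injection only if the second injection waits for it. As written, nothing makes it wait. The controls that do exist act once an event has occurred and been recognized. They do not cover a reaction that has yet to appear, and they set no trigger for untreated Grade 1 or 2 events or for a shift in an assay that has no threshold.

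**Working it through.** The plan states no timing figure to reproduce, so this check sets the text against a range of dosing schedules.

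**1. What the text allows.** With even spacing of s days and a review on day R, the number of further boys dosed before review is min(5, ceil(R/s) − 1). For R = 41 this is 5 at 7-day spacing, 2 at 14 days, 1 at 30 days and 0 at 61 days. The permitted range is 0 to 5.

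**2. When the review could fall.** The visit window in section 6.7 is 7 working days, which is 9 to 11 calendar days. The day 30 visit can therefore fall as late as day 39 to 41. A meeting 14 days later (an assumption) falls on day 53 to 55.

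**3. Enrollment period.** Section 11.5.3 gives Winter 2014 to December 2015, and section 5.0 cites a paper available in October 2014. From the end of October 2014 to the end of December 2015 is 426 days; from 1 March to 1 December 2015 is 275 days. The range used is W = 270 to 430 days.

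**4. Chance that at least one further boy is dosed before review.** Assume six independent uniform dosing dates over W days. Then P = 1 − (1 − R/W)^6.

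| Review on day | W = 270 | W = 365 | W = 430 |
|---|---|---|---|
| 30 | 51% | 40% | 35% |
| 39 | 61% | 49% | 43% |
| 41 | 63% | 51% | 45% |
| 53 | 73% | 61% | 55% |
| 55 | 75% | 62% | 56% |
| 90 (late, but permitted) | 91% | 82% | 76% |

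With u = R/W, the mean number of further boys dosed by day R is 6u − u^6. For day 39 this is 0.87, 0.64 and 0.54. The chance that all six are dosed by day 39 is 6u^5 − 5u^6, about 0.03% or less.

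If dates are evenly spaced instead, the gaps W/5 are 54, 73 and 86 days, and a review by day 53 already precedes the second boy.

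**5. Effect on severe events.** This was simulated with the halt working and permanent, onset uniform over 30 days, and a hold to day 53. Expected Grade 3 or higher events:

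| W, risk per boy | No hold | Hold, later dates shifted | Hold, waiting boys dosed together at release |
|---|---|---|---|
| 270, 20% | 0.780 | 0.767 | 0.784 |
| 270, 30% | 0.963 | 0.934 | 0.967 |
| 365, 10% | 0.478 | 0.475 | 0.478 |
| 365, 20% | 0.769 | 0.760 | 0.770 |

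Over all cases run (risk 10%, 20% and 30%; W = 270, 365 and 430), the change ranges from about 0.03 fewer to 0.004 more. The small increases occur only when waiting boys are dosed together at release.

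**6. Findings below the halt threshold.** The documents give no rate. Let q be the chance that the first boy's day 30 data hold a finding that would change later dosing. The chance that it exists and a further boy is already dosed is q × P. For q = 5%, 10% and 20% (illustrative only), this is 2–3%, 4–6% and 9–12% by day 39, and 3–4%, 5–7% and 11–15% by day 53.

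**7. Prior level of concern (section 7.2).** Total dose: 2.4/1.2 = 2 times the earlier maximum. With an equal split over three muscle groups (an assumption), each gets 1.2 × 10^12 / 3 = 4 × 10^11 vg/kg per limb, below the 6 × 10^11 already given per quadriceps. Mouse margin: 2.0 × 10^13 / 2.4 × 10^12 = 8.3.

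**8. Delay from a hold to day h.** Under uniform dates the mean added wait for the second boy is h − (W/7)[1 − (1 − h/W)^7]. For h = 53 this is 22.8, 18.2 and 16.0 days; for h = 55 it is 24.3, 19.5 and 17.1 days.

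**The case against.** The case against a change is substantial.

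- **Small gain in severe events.** With the halt in place the gain is close to nil, and natural spacing may already put the review first. A review by day 39 would on average still precede more than four of the five later boys.
- **Existing cover.** The DSMB can meet or ask for reports whenever it wishes, and could request staggered dosing at its meeting before initiation. The safety monitor sees laboratory data. Untreated mild events do appear in the DSMB listings. An immune finding could be judged an important laboratory finding and trigger the halt.
- **Low prior concern.** Section 7.2 reports no dose-limiting toxicity at the two Becker doses, and section 5.0 says that the FDA permitted treatment of this population.
- **Model.** Independent uniform dates are a rough model for inpatient procedures under sedation at one site, and section 11.5.3 describes enrollment, not dosing. The shortest window used, 270 days, is slightly below the shortest derived, 275.

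All of this stands as a limit on the size of the point. None of it makes the second injection wait for the first boy's review.

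A reader might infer that the halt rule is defective, or that the plan intends to treat several boys at once. The documents support neither: the halt covers related severe events, and the text is silent on spacing. A reader might also infer that a hold would remove the risk. It would not, because results pending at release can arrive after the second boy is dosed, and a late reaction can still appear.

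**Conclusion.** The gap is in the text and needs no assumption: the early review has no deadline and no later dose depends on it. How often it would matter depends on the unknown dosing dates. Under random dates the chance is roughly two in five to three in five for a review on day 39, and higher if the meeting slips. With boys about 8 weeks or more apart and a prompt meeting, it does not arise.

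The expected reduction in severe events is very small. The real value is that the DSMB would see slower or milder findings, including the first post-dose circulating follistatin value if available, before a second child is committed. That value cannot be quantified from the documents. This is a worthwhile, inexpensive improvement to the order of dosing, not an error in the stopping rule. Confidence is medium.

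**What to change.** State in sections 7.4 and 12.1 that no second subject receives gene transfer until the DSMB has reviewed the first subject's data through day 30 and recorded a recommendation to proceed. Those data are adverse events, safety laboratory tests, and the immunology and circulating follistatin results then available. Hold the meeting within 14 days of that visit. Add that subjects waiting at release are dosed one at a time, at a minimum interval agreed with the DSMB. Without that clause, dosing together at release can cancel the small gain. Send results still pending to the DSMB when they arrive.

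Do the second boy's baseline biopsy only after release, so that no child has an invasive procedure that proves needless. If his other screening starts around the first boy's day 30, release on day 53 to 55 falls 23 to 25 days into the 45-day screening window and leaves 20 to 22 days for biopsy and injection.

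The cost is a short addition to two sections, using a meeting already planned, plus an interval to agree. Release falls on about day 37 (visit on time, meeting a week later) to day 55, so the second boy is dosed no sooner than about 5 to 8 weeks after the first. The average added delay is about 16 to 23 days for a day 53 release if dates are random (about 17 to 24 for day 55), and essentially none if boys are already about 8 weeks apart. In a progressive disease that delay is a real cost, but a modest one.
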